#### **If BP mildly elevated ( $\geq 140/90$ )**

- Alert is generated through the BabyScripts app for both or either diastolic alone or systolic alone readings above the threshold
- Subject receives an immediate text and an email message via BabyScripts letting the subject know they have a mildly elevated BP reading and asking the subject to complete a symptom checklist (headache, vision changes, severe abdominal pain, swelling of hands and face, shortness of breath/anxiety) directly in the app. If they have no symptoms, the "no symptoms" icon must be checked in the app. (*Appendix 8a and 8b*)
- Subject is instructed via BabyScripts app to recheck BP in 10 minutes
- The MFM staff member or provider is alerted by the BabyScripts call center within 4 hours
- MFM staff member or provider calls subject for further evaluation and instructions:
  - If this is new onset and subject has no symptoms, then subject will be scheduled for an office visit in 1-3 days.
  - If has chronic or known history of hypertension and subject has no symptoms, then they will continue monitoring BP per study protocol.
  - If subject has symptoms, she will be referred to OB triage

#### **If BP critically elevated ( $\geq 160/110$ )**

- Alert is generated through the BabyScripts app for either diastolic alone or systolic alone readings or if both readings are above the threshold

- Subject receives an immediate text and email message via BabyScripts letting subject know they have a critically elevated BP reading and asking the subject to complete a symptom checklist directly in the app. If they have no symptoms, the “no symptoms” icon must be checked in the app.
- On-call MFM staff is alerted by BabyScripts call center within 60 minutes [14-19].
- Provider (or nurse – see 2nd bullet below) calls subject for further evaluation and instructions within 45 minutes:
  - If this is new onset hypertension irrespective of symptoms, the subject is referred to OB triage and instructed to present without delay.
  - If subject also has a chronic or known history of high BP, but no other symptoms, then a RN reviews the BP measurements, discusses with the clinic or on-call MFM physician, and contacts the subject with the provider’s recommended instructions.

For the subjects in the rBPM study arm, acceptability and user experience data will be collected via on-line REDCap questionnaire ~ 21 – 28 days after study enrollment, or within one week of the subject’s completion of the study. A unique link to the REDCap questionnaire will be sent via email to the subject. If the questionnaire is not completed within 1 week of being sent, a reminder email to complete the survey will be sent weekly for a maximum of 3 weeks. Completion of this on-line survey is expected to take <= 5 minutes.

Per standard of care, the rBPM study arm subject’s initial postpartum OB provider visit will be scheduled either at ~1 week after delivery for high risk subjects and at ~4-6 weeks after delivery for subjects with a low risk of postpartum complications. Additional follow-up medical care visits may be scheduled at the discretion of the provider and the subject. All follow-up medical care, regardless of the study arm, will be at the expense of the individual subject.

The subjects randomized to the experimental study arm will be provided with a specialized BP cuff/monitor at no cost. The subject will be able to keep the BP cuff/monitor for personal use after they have completed the study. The subject does not need to return the monitor.

The subjects randomized to the SOC study arm will not be provided with specialized BP cuffs and monitors, and will not download the BabyScripts app. For subjects that are considered to be high risk within this study arm, with high blood pressure or a history of high blood pressure during or before pregnancy, they may be instructed to check home blood pressures at the discretion of their primary provider. The subject’s postpartum OB provider visit will be scheduled either at ~1 week after delivery for high risk subjects and at ~4-6 weeks after delivery for subjects with a low risk of postpartum complications. Additional follow-up visits may be scheduled at the discretion of the provider and the subject.

Study subjects will not receive any financial compensation for participating in this research study.

### **Outcome Measures**

1. Assess the feasibility and acceptability (patient adherence and satisfaction) of administering a rBPM intervention in the postpartum period particularly in a predominantly lower socioeconomic status population.
2. Evaluate the impact of rBPM on adherence to ACOG recommendations, the length of postpartum admission, occurrence of readmissions and length of stay for readmissions. The initial hospital admission

stay could be reduced as a result of the provider discharging the patient when they know that the patient will be able to monitor their blood pressure at home (instead of keeping them to conduct additional monitoring in the hospital).

3. Assess the impact of rBPM intervention on emergency and urgent acute care utilization and rate of severe hypertension within first week postpartum and third week postpartum.

4. Assess impact of a rBPM intervention on total health care costs to the patient during the first eight weeks postpartum

4. Validate and calibrate previously developed predictive algorithm for postpartum high blood pressure complications.

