#### **Standard of Care (SOC) Arm**

Subjects randomized to SOC arm are provided with the appropriate standard of care depending upon their risk level (as determined by their individual provider or AHWFB Maternal-Fetal Medicine provider)

- High-risk women:
  - Scheduled in-person visit 1 week postpartum with their OB
  - Scheduled in-person visit 4-6 weeks postpartum with their OB
  - Additional visits as clinically indicated determined by the patient's provider(s).
  - Patients with high blood pressure may be instructed to check home blood pressures at the discretion of their primary provider
  - Blood pressure cuffs are not routinely provided by primary provider
- Low-risk women:
  - Typically scheduled in-person visit 4-6 weeks postpartum with their OB
  - Additional visits at patient/provider discretion

The individual subject's provider will perform all follow-up postpartum OB visits. The study team will not initiate the scheduling of any follow-up postpartum OB visits for either study arm (this is the responsibility of the individual subject). However, the study team members may encourage subjects to make and keep their 4-6 week postpartum visit. All physician/health care provider visits will be at the expense of the individual subject.

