### **Remote Blood Pressure Monitoring (rBPM) Arm**

Subjects randomized to rBPM arm receive the appropriate standard of care depending upon their risk level, as well as the remote BP monitoring app (BabyScripts) and Bluetooth enabled BP cuff/monitor, and will receive the following equipment and monitoring:

- High-risk women:
  - Scheduled in-person visit 1 week postpartum with their OB
  - Scheduled in-person visit 4-6 weeks postpartum with their OB
  - Additional visits as clinically indicated determined by the patient's provider(s).
- Low-risk women:
  - Typically scheduled in-person visit 4-6 weeks postpartum with their OB
  - Additional visits at patient/provider discretion
- Provided with a specialized, Bluetooth enabled BP monitoring cuff (Clinically Validated, A&D Medical Wireless Blood Pressure Monitor-Upper Arm (*Appendix 2*)
  - The standard BP cuff is designed to fit a wide-range of arm circumferences (8.6-16.5 inches) and can accommodate an individual with a BMI up to 45-50 kg/m^2.
  - An extra-large BP cuff will be available for women with larger arm circumferences (16.5-23.6 inches), or BMI >50 kg/m^2. The extra-large BP cuff is not Bluetooth enabled and the subject will need to manually enter BP data from the BP monitor into the BabyScripts app. We expect that this extra-large BP cuff will be needed for <10% of our subjects (based on historical data from other facilities utilizing BabyScripts app)
- Assistance with downloading BP monitoring smart phone app, BabyScripts™ (*Appendix 3a and 3b*)
- Verbal and written instructions, to conduct BP checks at home (with reminder notifications sent via the BabyScripts app): (*Appendix 4*)
  - Twice daily on days #1 through #16 (day #1 = day after hospital discharge)
  - At least once daily on days #17 through # 21
  - Due to the customization limitations of the Babyscripts app, subjects will receive twice daily reminder notifications for the duration of the study enrollment period (21 days); however, the NEST coordinators will remind the subjects that we are only asking them to check their BP once daily on days #17 through #21.
- Subjects will be asked to demonstrate the accurate use of the BP cuff/monitor and the BabyScripts app for a study team member, prior to being discharged from the hospital. This is to evaluate their level of understanding, to confirm the BP cuff is the correct size, and that the equipment is working properly.

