- All BP measures and any alerts will be sent in real-time to a secure cloud-based portal, DIANA. This portal will be accessible only to designated staff members. Clinically-relevant readings and symptoms initiate an alert to BabyScripts call center and then are communicated directly to AHWFB Maternal-Fetal Medicine staff
- AHWFB Maternal-Fetal Medicine on-call staff are available for response 24/7/365
- Acceptability and user experience data will be collected via on-line REDCap survey between 21-28 days after enrollment (*Appendix 5a and 5b*)

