The subject's education/training for participating in this research study is expected to take approximately 10 - 15 minutes, but the amount of time needed may vary based on the individual subject's level of understanding. After completing the training, a NEST Coordinator must observe a successful subject-directed trial of the rBPM equipment and app. The NEST Coordinator will document any identified barriers that may limit the subject's successful participation in the study.

The subject will use the specialized BP cuff/monitor to measure their BP twice-daily beginning on the morning of the day following hospital discharge. This day will be noted as "Day 1". Twice daily BP monitoring will continue through Day 16. Then, starting on Day 17, the subject will need to obtain their blood pressure only once daily in the morning, and continuing daily through Day 21. Subject's BP measurements will no longer be transmitted via BabyScripts app beginning on Day 22. The subject will receive a reminder text via the BabyScripts app when it is time to obtain their BP. Due to the limitations for customization, the Babyscripts reminder notifications will be sent twice daily (one in the morning and once in the evening) for the entire 21 day study period. . It is expected that it will take the subject less than 5 minutes (after a 5-10 minute rest period that is recommended to for the most accurate reading) to obtain each BP measurement. The subject's BP measurements, and any alerts are sent in real-time to a secure cloud-based portal. If the subject's BP falls within the normal range ( $\leq 140/90$ ), they will receive notification via the BabyScripts app, that their BP reading is normal. Any clinically relevant BP readings (defined below) will initiate an alert to the BabyScripts call center staff, who then communicates directly with a member of AHWFB Maternal-Fetal Medicine (MFM) staff. An assigned (or on-call) MFM staff member is available for response 24/7/365. While BabyScripts acts in real-time to alert the provider, any issues with wait time, unanswered phone lines, etc. may lead to delays to when the subject can expect to hear from the provider. Alert calls received from BabyScripts are documented in the subject's EMR.

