### **Clinical outcomes**

#### Primary:

We anticipate a significant increase in proportion of women having their blood pressure monitored according to ACOG guidelines for obtaining BP measures (obtain BP with 72 hours of discharge and maintain monitoring through 7-10 days for all women with hypertensive disorders of pregnancy (HDP)), with an absolute difference of >30% between those randomized to usual care versus remote BPM for within 72 hours and an absolute difference of 30% for continuous monitoring through 10 days (60% for usual care vs 90% intervention arm in those with higher risk - antepartum/delivery HDM).

Among all women (with and without HDP) we anticipate an absolute difference of 60% between those randomized to usual care versus remote BPM for obtaining blood pressure measures within three weeks of discharge (30% usual care vs 90% intervention arm for low and high risk women combined). We hypothesize that the disparity in obtaining these measures, according to insurance status, will be reduced.

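### Severe hypertension is to be judged between arms whose blood pressure is captured very differently, which biases that comparison against rBPM; a narrower gap may under-count guideline adherence in the SOC arm

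*Combined protocol and SAP*

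**What the plan says.** **The outcome.** Outcome Measures, item 3, lists the "rate of severe hypertension within first week postpartum and third week postpartum" beside emergency and urgent care use. No cut-off, setting or data source is given. The value 160/110 appears only as the app's higher alert level.

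**rBPM arm.** Women measure "Twice daily on days #1 through #16 (day #1 = day after hospital discharge", then "At least once daily on days #17 through # 21". The section on the rBPM arm adds: "All BP measures and any alerts will be sent in real-time to a secure cloud-based portal, DIANA". Under Interventions and Interactions, "Alert calls received from BabyScripts are documented in the subject's EMR". The two alert sections send some of these women to an office visit or to OB triage.

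**SOC arm.** There is no study cuff and no app. High-risk women have visits at about 1 week and at 4-6 weeks. For low-risk women the entry is "Typically scheduled in-person visit 4-6 weeks postpartum with their OB". High-risk SOC women with high blood pressure, or a history of it, are covered by this provision: "they may be instructed to check home blood pressures at the discretion of their primary provider". The Background section puts attendance at recommended in-person postpartum visits below 50% in this population.

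**Guideline adherence.** The primary clinical outcome anticipates "an absolute difference of >30% between those randomized to usual care versus remote BPM for within 72 hours" among women with hypertensive disorders of pregnancy (HDP). It also anticipates 60% against 90% for monitoring through 10 days and, among all women, 30% against 90% for a reading within three weeks of discharge.

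**Data.** The Analytical Plan's list of EHR measures does not name post-discharge blood pressure. A later sentence says EHR, BP and billing data will be linked, without saying what BP means in each arm. Only rBPM women receive a follow-up questionnaire.

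**The concern.** A severe reading can be counted only if someone takes a reading. One arm is prompted to take many and transmits them all. The other has at most one scheduled contact before week 4, and none in week 3. If the true risk is the same, more cases will be found in rBPM. A real benefit could be hidden or reported as harm, and a larger sample would only make the false difference more precise. Multiple imputation as appropriate, which is all the Analytical Plan offers, does not settle this, because being measured depends on arm and probably on symptoms.

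A second, smaller issue concerns adherence. If SOC women check at home and the study never learns of it, SOC adherence is recorded too low and the rBPM advantage looks too large.

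**Working it through.** The plan states no expected rate of severe hypertension and no alpha, so it has no figure to reproduce. What follows is illustration from stated inputs.

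**1. Scheduled readings, rBPM.** Days 1-16: 16 x 2 = 32. Days 17-21: 5 x 1 = 5. Total 37. First 7 days: 7 x 2 = 14. Days 15-21: 2 x 2 + 5 = 9. These days run from discharge and the outcome runs from delivery, so postpartum week 1 holds fewer than 14 home readings.

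**2. Scheduled contacts, SOC.** Week 1: about one visit for high-risk women, none for low-risk women. Week 3: none for either group.

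**3. Capture model.** Observed rate = true risk x probability of capture. With equal true risk, the observed ratio (rBPM to SOC) is the ratio of capture probabilities. The plan's anticipated proportions with a blood pressure obtained serve as capture probabilities; this is my assumption.
- 30% and 90% (all women, three weeks): 0.90 / 0.30 = 3.0.
- 60% and 90% (HDP women): 0.90 / 0.60 = 1.5.
- A true halving of risk: 0.5 x 3.0 = 1.5, an apparent excess; or 0.5 x 1.5 = 0.75, a diluted benefit.

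**4. Chance of a significant false excess in rBPM.** Two-sided 0.05 (assumed), 1000 per arm, equal true risk. The 60% figure comes from the HDP subgroup, which is smaller than 1000 per arm, so the last column shows only what that capture gap would do at full sample size.

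| True risk (assumed) | Capture 30% vs 90% | Capture 60% vs 90% |
|---|---|---|
| 1% | 41% | 12% |
| 2% | 69% | 20% |
| 3% | 86% | 27% |
| 5% | 98% | 42% |

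**5. Symptomatic presentation.** Let a share s of severe cases present with symptoms and be recorded in either arm. Capture becomes s + (1 - s) x c.

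| s (assumed) | c = 30% vs 90% | c = 60% vs 90% |
|---|---|---|
| 50% | 0.950 / 0.650 = 1.46 | 0.950 / 0.800 = 1.19 |
| 75% | 0.975 / 0.825 = 1.18 | 0.975 / 0.900 = 1.08 |

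**6. Second model, per reading.** Assume a 0.5% chance that any one reading is severe. The chance of at least one is 1 - (1 - 0.005)^n if readings are independent; a beta-binomial model with within-woman correlation 0.3 gives a lower bound.
- Week 1, n = 14: 6.8% down to 2.5%. Against 0.5% for a single SOC reading, the ratio is 6.8 / 0.5 = about 14, down to 2.5 / 0.5 = 5.
- Days 15-21, n = 9: 4.4% down to 2.0%, against no scheduled SOC reading.

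This model assumes full adherence and no symptom-driven visits, so I treat it as confirming direction only.

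**7. Adherence in HDP women.** Suppose the 60% for usual care excludes home checks, and a share h of the remaining 40% did check at home. The SOC figure becomes 60 + 40h and the difference is 90 - 60 - 40h = 30 - 40h points: 26, 20 and 10 points at h = 10%, 25% and 50%. The documents give no value for h and do not say that the 60% excludes home checks.

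**The case against.** The strongest defence on severe hypertension is that it carries no hypothesis and no primary or secondary label, so little may hang on it. Week 1 also includes inpatient time, when both arms are measured alike, and high-risk SOC women have a visit then. Many severe cases would present with symptoms in either arm. All of this stands, and it reduces the size, most clearly in week 1. It does not change the direction, and it does little for week 3.

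A reader might multiply up all 37 readings and infer a spurious ratio of 7 to 34 (3.5% to 16.9%, against 0.5%). The outcome names weeks 1 and 3, not the whole 21 days, and the 0.5% per reading has no source in the documents. The plan itself targets only 70% adherence to two readings a day in the first two weeks. That range should not be cited.

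A reader might also infer that the primary adherence comparison as a whole is biased towards rBPM. The documents do not support this. Getting blood pressure measured is what the intervention is meant to change, so most of the gap is its intended effect. SOC contact is scheduled by risk level and not left to chance, study cuffs are not given to that arm, and home checks are discretionary and limited to women with high blood pressure or a history of it. The Primary Objective gives its windows without distinguishing arms, and the linkage sentence leaves room for SOC readings. What remains is that no stated route brings SOC home readings in.

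Finally, a reader might suppose that encounter records or HDP readmission give an unbiased comparison. They do not fully: app alerts are written to the EMR and prompt office and triage visits.

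**Conclusion.** The point holds for severe hypertension. Capture depends on arm, the bias runs against rBPM, and week 3 is the worse window. The size cannot be fixed from the documents. Under the assumed capture rates, the false ratio is 1.5 to 3.0, falling to about 1.1 to 1.5 if 50-75% of severe cases are recorded through symptoms in either arm. These figures rest on reading the plan's anticipated measurement rates as capture probabilities and on equal true risk.

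For guideline adherence, only a narrow point holds: SOC adherence among HDP women may be under-counted, by an unknown amount, because home readings have no stated route into the data. The primary clinical outcome is not invalidated.

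**What to change.** **Severe hypertension**
1. State the threshold and data source for the outcome, and whether inpatient readings count.
2. Report app-detected severe hypertension descriptively, in the rBPM arm only.
3. Base any comparison between arms on dated EHR readings from encounters in both arms. Flag encounters triggered by an app alert and add a sensitivity analysis that excludes them.
4. Apply the same caution to HDP readmission and acute-care use, since alerts can also lead to these contacts.
5. State in advance that a higher detected rate in rBPM is not evidence of harm.

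**Guideline adherence**
1. Add dated post-discharge EHR blood pressures to the extraction list in the Analytical Plan.
2. Align the windows. The Primary Objective uses 72 hours and seven days from discharge, and three weeks postpartum; Clinical outcomes uses 72 hours, 7-10 days or 10 days, and three weeks from discharge.
3. Use one definition in both arms: at least one reading in each window.
4. E-mail SOC women a short REDCap form asking for dated home or outside checks. Use the answers in a sensitivity analysis beside the device and EHR result.

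**Cost.** Wording, one added extraction item, an alert flag and one automated survey. SOC answers will be recalled and incomplete, and the hypothesised 30-point gap may shrink. Excluding alert-triggered encounters removes some true rBPM events, so that analysis should not be the only result. Home readings that are never asked for may not be recoverable later, so the survey is the step to start first.

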### **Feasibility and acceptability outcomes**

#### Primary:

Among those randomized to the intervention arm, at least 90% will have a smartphone and will be able to have the remote BPM app loaded onto their phone, prior to discharge. We hypothesize an absolute difference of no more than 10% (e.g., 85% vs 95% with a smartphone) according to insurance status (Medicaid or uninsured vs. private insurance).

Remote BPM will be successfully integrated into patient care as evidenced by at least 90% adherence to a median of at least one blood pressure reading/day for three weeks and 70% adherence to obtaining a median of two blood pressure measures for initial 2 weeks postpartum. We hypothesize an absolute difference in adherence, according to patient insurance status of <15%.

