### **Background, Rationale, and Context**

Despite advances in perinatal care in the U.S., maternal mortality has more than doubled over the past two decades, with substantial racial and socioeconomic disparities observed.[1] Hypertensive disorders of pregnancy (HDP) are a leading cause of perinatal morbidity and mortality, with up to 20% of maternal deaths attributed to preeclampsia.[2] In the traditional postpartum care model, many women are not seen for follow-up until six weeks postpartum, with the highest risk women typically scheduled for follow-up three to seven days after discharge. Thus, the postpartum period is a time of particular susceptibility for maternal morbidity and mortality resulting from undiagnosed or inadequately managed HDP.[3] Women from lower socioeconomic status (SES) groups, as well as racial and ethnic minority groups, disproportionately experience an increased risk for adverse consequences from HDP.[4] To mitigate this risk, the American College of Obstetrics and Gynecology (ACOG) recommends blood pressure monitoring (BPM) at 72 hours and through 7-10 days postpartum for women with HDP.[5]

Postpartum readmission for HDP is not limited to antenatally diagnosed HDP; women at “low-risk” account for a significant proportion of readmissions for HDP.[6] ACOG guidelines for postpartum care in lower-risk women recommend an initial postpartum visit by three weeks and a final comprehensive visit by 12 weeks postpartum.[7] However, the majority of readmissions for postpartum HDP occur prior to three weeks, suggesting that this care model is likely inadequate for many women and may contribute to missed or delayed diagnosis and treatment of HDP. In our own, highly diverse patient population, with nearly two-thirds of pregnancies covered by Medicaid or without insurance, compliance with recommended in-person, postpartum visits through this period, among women with higher and lower risk, is less than 50% (internal data).

Given the postpartum risks, women with known HDP experience increased length of stay during their initial postpartum admission.[8] While the increased length of stay has been associated with decreased readmission for HDP, it has also been associated with a significant increase in delivery hospitalization charges.[8] Remote BPM in the postpartum period has been proposed as an intervention to achieve increased monitoring without extending inpatient length of stay.[9]

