### **Subjects selection criteria**

### **Inclusion Criteria**

- Women that received prenatal care at one of the AHWFB OB/MFM outpatient clinic locations (Downtown Health Plaza, Clemmons Plaza, and Shepherd Street)
- Women that delivered an infant(s) at The Birth Center at AHWFB
- Women that delivered an infant(s) at home or outside facility, and were transported to AHWFB and received postpartum care in The Birth Center
- Currently resides in Forsyth County, NC
- 18 years of age or older
- Able to read and understand either English or Spanish
- Owns or has daily access to a smartphone (iOS or Android operating system) and Wi-Fi or monthly mobile data plan

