### **Exclusion Criteria**

- Women that delivered an infant(s) at any location other than The Birth Center at AHWFB
- Women that did not receive postpartum care at The Birth Center at AHWFB
- Resides outside of Forsyth County, NC
- Under 18 years of age
- Unable to read or understand either English or Spanish
- Does not own or have daily access to a smartphone (iOS or Android operating system)
- Owns a smartphone but does not have Wi-Fi or monthly mobile data plan

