## **Human Subjects Protection**

## **Subject Recruitment Methods**

A study staff member will review the daily prenatal clinic schedules at all 3 AHWFB locations (Downtown Health Plaza, Clemmons Plaza, and Shepherd Street) to screen patients for eligibility. The study staff member will then notify the designated clinic staff of the eligible patients that should be offered the opportunity to watch the SMART-BP informational video at some point during a prenatal clinic visit at  $\geq 24$  weeks gestation. Additional study subjects may be identified using daily census reports of the postpartum units in WakeOne (Epic).

Routine inpatient visits by our NEST Coordinators typically occur on the postpartum unit after delivery and before the patient is discharged from the hospital. If a patient is not in her private room at the time of the visit, for example, if she is visiting her baby in the NICU, the NEST Coordinator typically contacts these patients via phone, or may approach them in the NICU (only if appropriate). These efforts are made to ensure a patient that was not enrolled during a prenatal clinic visit is not excluded from the study if they are not physically in their room at the time of the NEST Coordinator's routine postpartum visit. If the patient is interested in participating in the study, the NEST Coordinator will offer the patient the opportunity to view the SMART-BP informational video and review and sign the consent form on an iPad ideally, in the patient's postpartum room. These visits are conducted on weekdays only. The patients that were not enrolled during a prenatal clinic visit and are discharged prior to an inpatient visit by a NEST Coordinator will not be eligible for enrollment in this study.

Any study recruitment advertisements will only be displayed in The Birth Center location on the main campus of Atrium Health Wake Forest Baptist and the prenatal clinics located at Downtown Health Plaza, Clemmons Plaza, and Shepherd Street.

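### The smartphone part of the first primary feasibility criterion is settled by the entry rules, and the median adherence rule does not measure persistence over the 21-day programme

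*Combined protocol and SAP*

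**What the plan says.** All references are to the combined protocol and SAP.

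- **Access criterion** (Feasibility and acceptability outcomes, Primary). The denominator is the intervention arm, in which "at least 90% will have a smartphone and will be able to have the remote BPM app loaded onto their phone, prior to discharge". The accompanying hypothesis is an "absolute difference of no more than 10% (e.g., 85% vs 95% with a smartphone) according to insurance status", comparing Medicaid or uninsured women with privately insured women.
- **Entry rules.** Inclusion Criteria require that a woman "Owns or has daily access to a smartphone (iOS or Android operating system) and Wi-Fi or monthly mobile data plan". Exclusion Criteria remove women who lack either the phone or the data connection.
- **Adherence criteria** (same Primary section). Successful integration into care is to be shown by two thresholds. The first, for the whole programme, is "at least 90% adherence to a median of at least one blood pressure reading/day for three weeks". The second concerns twice-daily measurement and is set lower: "70% adherence to obtaining a median of two blood pressure measures for initial 2 weeks postpartum". The section does not say whether the median is taken per woman, per week or per day across women. It does not say how a day without a reading counts, or that readings must continue to day 21. The Analytical Plan has only a general sentence on missing data.
- **Requested schedule** (Remote Blood Pressure Monitoring (rBPM) Arm; Interventions and Interactions). Two readings a day on days 1 to 16 and at least one a day on days 17 to 21, with day 1 the day after discharge.
- **Set-up after discharge.** Methods and Measures provides for prenatal enrollees who go home on a weekend or holiday without their cuff and instructions: the cuff goes by courier and a coordinator telephones afterwards. Subject Recruitment Methods says of the coordinators' inpatient visits: "These visits are conducted on weekdays only".

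**The concern.** Feasibility is the first listed objective, and the background justifies the trial by the lack of feasibility evidence in lower-income women. Women without a phone or data plan are excluded before randomisation, so a phone-access rate among randomised women, overall or by insurance status, says almost nothing about access in the population of interest. A median of daily counts is blind to what happens on nearly half of the days, so it can class a woman who gave up monitoring mid-way as adherent. A favourable result on these primary criteria could then be read as evidence of equal access and of sustained 21-day monitoring, when neither had been shown.

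**Working it through.** The plan attaches no calculation to these criteria, so there is no stated figure to reproduce. The checks apply its own rules.

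**1. Smartphone component.** Entry requires smartphone and data access. Among correctly enrolled women, access is therefore about 100% in each insurance group and the difference about 0 points. The illustrated 85% vs 95% cannot arise. App loading before discharge is not implied by eligibility and can fail.

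**2. The 85%/95% example against the 90% target.** With p the share of randomised women on Medicaid or uninsured, the overall rate is 0.85p + 0.95(1 - p) = 0.95 - 0.10p. This equals 0.90 at p = 0.50 and is lower for any larger p. The background describes the institution's patients, "with nearly two-thirds of pregnancies covered by Medicaid or without insurance". If that mix held among randomised women (an assumption), the rate would be 2/3 x 85% + 1/3 x 95% = 88.3%.

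**3. Readings requested.** 16 x 2 + 5 x 1 = 37 per woman at minimum, or 3,700 per 100 women.

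**4. Median of at least one a day over 21 days.** Take the median per woman, with an empty day as 0. It is the 11th of 21 ordered daily counts, so it is at least 1 when 11 days have a reading (11/21 = 52%).
- Last reading on day 11: median 1 at one reading a day, 2 at two a day. She passes.
- Last reading on day 10: median 0. She fails.
- Minimum readings to pass this criterion alone: 11 of 37 (30%).

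**5. Median of two over 14 days** (taken as days 1 to 14). This is the mean of the 7th and 8th ordered counts. With two readings on k days and none on the rest, k = 7 gives (0 + 2)/2 = 1 and k = 8 gives 2. Eight days are needed (8/14 = 57%).

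**6. Both thresholds together, read as 90% and 70% of women, per 100 women:**
- 70 women take two a day on 8 days and one a day on 3 days, stopping after day 11: 70 x (16 + 3) = 1,330 readings. They pass both criteria.
- 20 women take one a day on days 1 to 11: 20 x 11 = 220 readings. They pass the first criterion only.
- 10 women take none.

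The first criterion is met by 90% and the second by 70%. Total readings are 1,330 + 220 = 1,550, and 1,550/3,700 = 42%. None falls on days 12 to 21.

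**7. A less extreme pattern** (assumption: days are independent with a constant probability). The first threshold is reached when the daily chance of any reading is about 0.64. The second is reached when the daily chance of two readings is about 0.60, with other days empty.

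**8. Other readings of the median.**
- Empty days dropped: one day with a reading is enough.
- Week by week: a woman taking two a day to day 11 has medians 2, 2, 0 and fails in week 3.
- Across women on each day: a cohort that all stops after day 11 passes on 11 of 21 days.

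The result therefore turns on a choice that the plan does not state.

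**The case against.** Several stronger inferences are tempting, and the documents do not support them.

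- **That the whole access criterion is untestable.** It is joint with app loading before discharge, which can fail. Entry also rests on ownership or daily access, and prenatal enrolment can occur from 24 weeks, so access at discharge is close to 100% rather than fixed at it.
- **That weekend discharge makes the criterion fail by design.** Only prenatal enrollees who miss a coordinator visit are affected, and the documents give no number. This makes the target harder to reach, not easier. Such misses are real information about delivery, but they reflect staffing rather than the women's ability to use the tool.
- **That 85% and 95% contradict the target.** They illustrate a maximum gap and are not forecasts. The two-thirds mix belongs to the institution; the mix among randomised women is not stated.
- **That 11 single readings make a woman fully adherent.** She fails the two-a-day criterion. With both thresholds applied, the constructed example needs 42% of readings, not 30%.
- **That feasibility and equity go unmeasured.** App loading, the adherence gap by insurance status, satisfaction by insurance status and the guideline-window outcomes are all still measured. Monitoring to day 11 covers the 7-10 day window in the primary clinical outcome.

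It can also be said that these are descriptive targets in one arm and leave the randomised comparison untouched. That is correct. They are nevertheless labelled primary, and the plan makes them its evidence of successful integration.

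**Conclusion.** The point holds in a limited form. The smartphone component and its insurance contrast are uninformative among randomised women; the app-loading component is not. The 85%/95% example averages below 90% only if more than half of the randomised women are Medicaid or uninsured, which is likely on the institution's figures but not established. The adherence medians do not measure persistence over 21 days: both thresholds can be met with 42% of requested readings and none after day 11. That figure is a constructed possibility, not a prediction. It assumes a per-woman median with empty days as 0, and 90% and 70% as proportions of women. If the sponsor intended another reading of the median, the answer changes, so the definition has to be fixed in either case. The defect concerns the planned 21-day programme, not the shorter guideline window.

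**What to change.** 1. Drop the smartphone target and its insurance contrast among randomised women. Report app loading by insurance status, separately for women set up before discharge and those set up by courier and telephone.
2. Where screening allows, report the number and insurance status of otherwise-eligible women excluded for lack of a smartphone or data access. This is what speaks to unequal access.
3. Replace the medians by each woman's share of scheduled days with the required readings: days 1 to 21 with at least one, and twice-daily days (1 to 16) with at least two. Use all women randomised to rBPM as the denominator and count days without data as not done.
4. Prespecify both the per-woman cut-off and the proportion of women who must reach it (90% and 70%).

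On these measures, the women in the example who pass both median criteria score 11/21 = 52% and 8/16 = 50%, so early stopping becomes visible.

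Cost: readings already reach the study portal, so item 3 needs only new wording before analysis. Item 2 needs more. The protocol describes screening from clinic schedules and no log of phone or data status, so that information may be incomplete for women who never consent. Reported adherence will be lower than under the median rule. The monitoring schedule is unchanged.
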